#### **LEAP Siblings**

The primary endpoint is the rate of peanut sensitization in younger siblings who resided in the home of the LEAP participant on or before LEAP Visit 60, as assessed in the current LEAP Trio study. The main comparison is of the sensitization rate between the younger siblings of LEAP consumers and LEAP avoiders.

This comparison will be made by a logistic regression model with a random family effect included to account for the clustering of siblings within family units and the analysis of multiple younger siblings. This comparison evaluates whether the younger siblings of the LEAP consumers are at higher risk of peanut sensitization compared to the younger

siblings of LEAP avoiders due to the environmental exposure to peanut in conjunction with a lack of peanut consumption.

Additional analyses will be done in older siblings.

Secondary Endpoint	LEAP Participant Analysis	LEAP Sibling Analysis	LEAP Parent Analysis
Clinical 1,2,3,4*	The amount of peanut consumption, SCORAD, skin- prick test wheal sizes, and specific-IgE measurements including IgE to Ara h2 and other components will be compared between LEAP avoiders and LEAP consumers using parametric and non- parametric tests (e.g. Wilcoxon and t-test). The data will first be tested to determine normality. If the data are not normal then a Wilcoxon test will be run. If the data are normal then tests will be run to determine if the variances are equal between the two groups. If the variances are equal, a two sample t-test assuming equal variances will be used; otherwise, a two sample t-test assuming unequal variances will be used.	The amount of peanut consumption, SCORAD, skin- prick test wheal sizes, and specific-IgE measurements including IgE to Ara h2 and other components will be compared between the siblings of the LEAP avoiders and LEAP consumers using linear mixed effects models with a random family effect included to account for the clustering of siblings within family units and the analysis of multiple siblings.	The amount of peanut consumption, skin-prick test wheal sizes, and specific-IgE measurements will be compared between the parents of the LEAP avoiders and LEAP consumers using linear mixed effects models with a random family effect included to account for the clustering of parents within family units.
5,6 ⁺	The prevalence of asthma, rhinitis and eczema will be compared between LEAP avoiders and LEAP consumers using a two-tailed, chi-squared test at the 0.05 level of significance.	The prevalence of asthma, rhinitis, and eczema will be compared between the siblings of the LEAP avoiders and LEAP consumers using a logistic regression model with a random family effect included to account for the clustering of siblings within family units and the analysis of multiple siblings.	The prevalence of asthma, rhinitis, and eczema will be compared between the parents of the LEAP avoiders and LEAP consumers using a logistic regression model with a random family effect included to account for the clustering of parents within family units.
7		The proportion of participants with peanut allergy will be compared between the siblings of the LEAP avoiders and LEAP consumers using a logistic regression model with a random family effect included to account for the clustering of siblings within family units and the analysis of multiple siblings.	The proportion of participants with peanut allergy will be compared between the parents of the LEAP avoiders and LEAP consumers using a logistic regression model with a random family effect included to account for the clustering of parents within family units.
8	The proportion of participants experiencing at least one	The proportion of participants experiencing at least one	
Protocol ITN	U/UAD	v /.0	10 December 2021

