## 4.2 LEAP SIBLINGS

## 4.2.1 Inclusion Criteria – LEAP Siblings

Individuals must meet *all* of the following criteria to be eligible for this cohort in the study:

- 1. Sibling of LEAP participant.
- 2. Willingness to participate in at least one study data collection (i.e. questionnaire, skin pricking testing, or blood draw).
- 3. Assent by child and informed consent by parent or legal guardian if child is younger than 16; siblings aged 16 and over will provide their own consent. For participants only returning a Questionnaire in any format, assent/informed consent will be implied. For participants only completing a telephone visit, assent/informed consent will be given verbally.

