#### 4.2.2 Exclusion Criteria – LEAP Siblings

There are no exclusion criteria for LEAP siblings.

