Exploratory endpoint #4 (household peanut consumption and concentration of peanut dust) will be compared between the families of the LEAP avoiders and LEAP consumers using linear mixed effects models with a random family effect included to account for the nesting of multiple family members within family units.

Younger and older siblings of LEAP participants will be analyzed separately.

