8.2.2.1. Computation of the Primary Endpoint

Peanut sensitization at V144 is defined as meeting at least one of the following criteria:

- a) Peanut specific IgE ≥ 0.35 kU/L
- b) Peanut specific IgE to individual peanut component Ara h2 ≥ 0.1 kU/L
- c) Skin prick test to peanut ≥ 3 mm.

LEAP Siblings who were born on or after the date of birth of the LEAP Participant will be classified as Younger Siblings. Questionnaire responses will be used to determine if the Younger Siblings resided in the home of the LEAP Participant on or before LEAP V60.

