8.2.2.2. Primary Analysis: Between-group comparison

The main comparison for the LEAP Siblings is the peanut sensitization rate at V144 between the Younger Siblings of LEAP Consumers and LEAP Avoiders in the ITT population who resided in the home of the LEAP Participant on or before LEAP V60. Younger LEAP Siblings with a missing peanut sensitization status will not be included in the analyses.

This comparison will be made by a logistic regression model with a random family effect included to account for the clustering of siblings within family units and the analysis of multiple Younger Siblings. This comparison evaluates whether the Younger Siblings of the LEAP Consumers are at higher risk of peanut sensitization compared to the Younger Siblings of LEAP Avoiders due to the environmental exposure to peanut in conjunction with a lack of peanut consumption.

The same statistical methodology will be repeated for all Younger Siblings in the ITT population and in the Younger Siblings in the PP population.

The same statistical methodology will be repeated for the comparison of the peanut sensitization rate at V144 between the Older Siblings of LEAP Consumers and LEAP Avoiders in the ITT population.

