The peanut sensitization status of LEAP Trio Siblings in the ITT populations will be analyzed using logistic regression models with a random family effect and possible fixed effects including treatment arm, whether Younger or Older sibling, age at V144, TEWL measurement, sibling history of eczema, whether resided in home of LEAP Participant on or before V60, peanut protein in bed dust at V144, peanut protein in bed dust of LEAP Participant at V60, peanut consumption of the sibling during the first year of life, and peanut consumption of LEAP Participant during the LEAP study. The fixed effects, along with possible interactions terms, will be evaluated for inclusion in the final logistic regression model.

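### The secondary sibling comparisons leave out age and sex, although both are collected and age varies widely within each sibling set: a cheap precision gain, not an error

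*Protocol*

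**What the plan says.** **The models.** In the Protocol 9.2.2 table, the sibling comparisons of peanut intake, SCORAD, wheal size and specific IgE are "compared between the siblings of the LEAP avoiders and LEAP consumers using linear mixed effects models with a random family effect included". For the binary outcomes, "The prevalence of asthma, rhinitis, and eczema will be compared between the siblings of the LEAP avoiders and LEAP consumers using a logistic regression model", again with a random family effect. SAP 8.3.2.2, 8.3.3.2, 8.3.4.2, 8.3.5.2, 8.3.6.2, 8.3.7.2, 8.3.8.2, 8.3.9 and 8.4.4.2 repeat this form. SAP 8.3.5.2 adds an ordinal mixed model for SCORAD categories. The co-primary sensitization model has the same content (SAP 8.2.2.2): "This comparison will be made by a logistic regression model with a random family effect included to account for the clustering of siblings". None of these names age or sex.

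**Who the siblings are.** "There are no exclusion criteria for LEAP siblings" (Protocol 4.2.2), and the inclusion criteria set no age range. "siblings aged 16 and over will provide their own consent" (Protocol 4.2.1), and Appendix 1, footnote 5, limits food challenges to siblings under 18, so older ones are foreseen. The challenge rules for children of 36 months or less (Protocol 6.7.1) can apply only to siblings, because LEAP participants must be at least 9.5 years old.

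**How they are grouped.** "Younger and older siblings of LEAP participants will be analyzed separately" (Protocol 9.2.2). The definition of Younger is broad: "LEAP Siblings who were born on or after the date of birth of the LEAP Participant will be classified as Younger Siblings" (SAP 8.2.2.1). The co-primary analysis also requires residence in the participant's home on or before LEAP Visit 60. The secondary analyses do not.

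**Where age does appear.** The exploratory factor models for sibling sensitization and sibling peanut allergy (SAP 8.2.2.3 and 8.3.9.2) list "possible fixed effects including treatment arm, whether Younger or Older sibling, age at V144, TEWL measurement" and other terms as candidates. Age and sex are summarised at V144 (SAP 6.2). The confounder-adjusted models in Protocol 9.2.1 and SAP 8.2.1.2 stand under LEAP Participants.

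**The concern.** Aeroallergen IgE and wheal size, SCORAD, rhinitis, asthma and peanut intake can all be expected to vary with age during childhood. If they do, age variation inside each sibling set goes into the residual and widens the confidence interval for arm. A chance difference in sibling age between the arms then moves the estimate with nothing in the model to absorb it.

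The plan is also uneven. LEAP participants, who fall in a limited age band, get a supporting analysis adjusted for age and gender. Siblings, who have no age limit, get none. Sex is in no sibling model, although Protocol 1.4 lists male sex, at least in childhood, among the risk factors for food allergy.

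The number of siblings is fixed by the LEAP families, so recruiting more cannot recover lost precision. Adding covariates only after an age imbalance has been seen would be open to challenge.

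**Working it through.** **1. The plan's own figure.** Protocol 9.3 states power of 83%, 79% and 73% for 8% v 17% sensitized at 90%, 80% and 70% enrolment. The pool is 222 + 207 + 80 = 509. I split the added 80 in proportion, giving 263 avoidance and 246 consumption; the documents do not give the split. At 90% this is 237 v 221.
- Pooled rate = (237 × 0.08 + 221 × 0.17)/458 = 0.1234.
- Null SE = √[0.1234 × 0.8766 × (1/237 + 1/221)] = 0.03076.
- Alternative SE = √(0.08 × 0.92/237 + 0.17 × 0.83/221) = 0.03081.
- Power = Φ[(0.09 − 1.96 × 0.03076)/0.03081] = 83.3%.

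The same formula gives 78.7% at 210 v 197 and 73.2% at 184 v 172. The stated figures reproduce. They involve no covariates and no clustering.

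**2. Age span of each set.** Protocol 3.1 gives example dates for the youngest and oldest participants.
- Youngest: 20 March 2009 minus 137 days is about 3 November 2008, so 60 months falls in about November 2013. A sibling in the home by then is at least about 4.3 years old when the study opens on 1 March 2018.
- Oldest: 2 February 2007 minus 332 days is about 7 March 2006, or 16.5 years at 31 August 2022. A Younger Sibling cannot be older than this.

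The co-primary set therefore spans about 4 to 16.5 years. The Younger set in the secondary analyses has the same ceiling but no floor from Visit 60. The Older set has no ceiling and extends into adulthood.

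**3. Linear models.** If age and sex explain a share R² of the variance, the SE is multiplied by √(1 − R²), and the gain equals having 1/(1 − R²) times as many siblings. Power from an assumed 80% base is Φ[2.80/√(1 − R²) − 1.96]. The documents give no R², so the range is assumed.

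| R² | SE falls by | Equivalent extra siblings | 80% power becomes |
|---|---|---|---|
| 5% | 2.5% | 5% | 82% |
| 10% | 5% | 11% | 84% |
| 20% | 11% | 25% | 88% |

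**4. Co-primary endpoint.** Logistic regression was simulated at 237 v 221 with marginal rates held at 8% and 17%, 10,000 runs per row and no family clustering. The age effect is assumed.

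| Age OR per SD | Power, arm only | Power, arm + age |
|---|---|---|
| 1.0 | 83.6% | 83.8% |
| 1.25 | 83.7% | 83.9% |
| 1.5 | 83.9% | 84.4% |
| 2.0 | 83.2% | 84.6% |
| 3.0 | 83.6% | 88.0% |

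The arm-only type I error was 4.2% to 4.9%, so the planned test holds its level.

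**5. Chance age imbalance.** The 95% range for the difference in mean age is ±1.96 × √(1/237 + 1/221) = ±0.18 SD, or ±0.64 years if the age SD is 3.5 years (assumed). A 0.18 SD difference multiplies the odds ratio by exp(0.183 × ln 1.25) = 1.04 at an age OR of 1.25 per SD, and by exp(0.183 × ln 2) = 1.14 at an age OR of 2.

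**6. Shift in the odds ratio from adjusting.** With 8% and 17%, the marginal OR is (0.17/0.83)/(0.08/0.92) = 2.36. Taking age as normal and solving for the arm intercepts that keep those marginal rates gives an age-conditional OR of 2.37 at an age OR of 1.25 per SD and 2.47 at an age OR of 2.

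**The case against.** **The analysis is valid as written.** Arm follows the family's randomisation, chance imbalance is already in the standard error, and type I error is held. Age and sex will be tabulated by cohort and arm (SAP 6.2), so an imbalance would be seen. All of this stands. A reader might infer that the sibling results are confounded by age; the documents do not support that.

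**Toddlers and adults are not mixed in one main comparison.** This also stands. One might infer from the open eligibility that each estimate pools toddlers with adults. Younger and Older Siblings are in fact modelled separately, and only the exploratory factor models pool them. A child of 36 months or less at opening was born in March 2015 or later, more than 6 years after the youngest participants, and the documents give no count of such siblings. The split still leaves a wide span inside each set.

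**Age is not absent from the plan.** True, but it is only a candidate term in exploratory, pooled models of sensitization and peanut allergy, and inclusion is decided from the data. Those models do not analyse IgE, wheal size, SCORAD, intake, asthma, rhinitis, eczema or TEWL as outcomes.

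**The size is assumed.** It is. No R², age SD or age-outcome slope is given, and no power is stated for any sibling secondary endpoint. The safety question also rests on sensitization and allergy, and the computed gain for sensitization is small.

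**Adjustment changes the odds ratio.** This carries little weight. The random family effect already makes it a conditional odds ratio, and step 6 shows only a small further shift. It is still a reason to leave the binary main models alone.

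**Conclusion.** The point holds as one of precision. The sibling comparisons for secondary endpoints 1 to 5 and 7 and for TEWL use arm and a family effect alone. Age at V144 and sex are available, and arm cannot affect them.

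For the linear models the SE would fall by about 2.5% to 11% if the two covariates explain 5% to 20% of the variance. The gain is near zero for any outcome they barely predict. For the co-primary endpoint the gain is about 0 to 1.5 power points up to an age OR of 2 per SD. It reaches about 4 points only at an OR of 3, which would be a very strong age effect.

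Two stronger readings fail. It does not follow that every sibling estimate is degraded, because that depends on age effects the documents do not report. Nor does it follow that the co-primary result is materially underpowered for want of an age term.

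The figures rest on the assumed R² and age effects, the proportional split of the 80 added siblings, and a simulation without clustering. The 458 siblings are the co-primary pool at 90% enrolment; the sizes of the secondary sets are not given.

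**What to change.** - **Linear and ordinal models.** In Protocol 9.2.2 and SAP 8.3.2.2, 8.3.3.2, 8.3.4.2, 8.3.5.2 and 8.4.4.2, add age at V144 (continuous) and sex as fixed effects to the linear sibling models. Do the same in the ordinal SCORAD category model in 8.3.5.2.
- **Binary outcomes and co-primary endpoint.** In SAP 8.3.6.2, 8.3.7.2, 8.3.8.2, 8.3.9 and 8.2.2.2, keep the stated model as the main analysis. Pre-specify the same model with age and sex as a supporting analysis, reported beside it.
- **Record the change** in SAP section 11.

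This needs no new data and no further siblings. The cost is amended wording, a little more analysis work, and a small shift in the conditional odds ratio in the adjusted logistic models, which the report should mention.

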#### 9.2.2 Secondary and Exploratory Endpoints

Secondary Endpoint	LEAP Participant Analysis	LEAP Sibling Analysis	LEAP Parent Analysis
	peanut-related adverse event will be compared between LEAP avoiders and LEAP consumers using a logistic regression model.	peanut-related adverse event will be compared between the siblings of the LEAP avoiders and LEAP consumers using a logistic regression model with a random family effect included to account for the clustering of siblings within family units and the analysis of multiple siblings.	
Exploratory 1	The proportion of participants with food allergies other than peanut will be summarized descriptively.	The proportion of siblings with food allergies other than peanut will be summarized descriptively.	The proportion of parents with food allergies other than peanut will be summarized descriptively.
3	Dietary assessments will be compared between LEAP avoiders and LEAP consumers using parametric and non- parametric tests (e.g. Wilcoxon and t-test). The data will first be tested to determine normality. If the data are not normal then a Wilcoxon test will be run. If the data are normal then tests will be run to determine if the variances are equal between the two groups. If the variances are equal, a two sample t-test assuming equal variances will be used; otherwise, a two sample t-test assuming unequal variances will be used. TEWL will be compared between LEAP avoiders and LEAP consumers using parametric and non-parametric tests (e.g. Wilcoxon and t-test). The data will first be tested to determine normality. If the data are not normal then a Wilcoxon test will be run. If the data are normal then tests will be run to determine if the variances are equal between the two groups. If the variances are equal, a two sample t-test assuming equal variances will be used; otherwise, a two sample t-test assuming unequal variances will be used; otherwise, a two sample t-test assuming equal variances will be used; otherwise, a two sample t-test assuming unequal variances will be used.	TEWL will be compared between the siblings of the LEAP avoiders and LEAP consumers using linear mixed effects models with a random family effect included to account for the nesting of siblings within family units and the analysis of multiple siblings.	

\*Secondary clinical endpoint #4 is only collected in LEAP participants and siblings of LEAP participants

+Secondary clinical endpoint #6 is only collected in the parents of LEAP participants

Exploratory endpoint #4 (household peanut consumption and concentration of peanut dust) will be compared between the families of the LEAP avoiders and LEAP consumers using linear mixed effects models with a random family effect included to account for the nesting of multiple family members within family units.

Younger and older siblings of LEAP participants will be analyzed separately.

## 9.2.3 Safety Analysis

Safety will be analyzed through the reporting and analysis of AEs. All AEs will be classified by body system and preferred term according to a standardized thesaurus. The severity of AEs will be classified using the NCI-CTCAE toxicity scale. The total number of events and the number of participants experiencing AEs will be summarized by body system and preferred term for each group and overall. Adverse events will also be summarized by maximum severity, relation to underlying disease, and relation to the study procedure for each group and overall. Separate summaries will be provided for serious AEs, procedure-related AEs, and AEs leading to study discontinuation.

## 9.2.4 Relevant Medical History

Relevant medical history within the past 12 months, including the existence of current signs and symptoms, will be collected for each body system.

## 9.2.5 Use of Medications

All medications taken by or administered to study participants beginning 30 days before enrollment and continuing throughout the study will be collected. All medications used will be coded according to the WHO drug dictionary. The number and percentage of participants receiving prior and concomitant medications/therapies will be presented overall and by medication class.

# 9.3 SAMPLE SIZE

# **LEAP Participants**

The sample size is based on the number of children likely to be available to enroll in the study. As shown in the Figure 1 LEAP Screening, Participant and Sibling Cohorts, there are 311 LEAP avoiders and 319 LEAP consumers (total 630) potentially eligible for enrollment. In the LEAP study, the rate of peanut allergy was 3.2% among consumers and 17.2% among avoiders at 60 months of age. We assume that the rates will not change markedly between month 60 and 144. We wish to detect a difference between the groups that are similar to that detected at 60 months. 88.5% of those potentially eligible enrolled in the follow on LEAP-On Study. We assume a lower percentage of those potentially eligible will enroll in this study.

For example, if 80% of those potentially eligible enroll, the true rate of allergy among LEAP consumers at 144 months is 6%, and the true rate of allergy among LEAP avoiders at 144 months is 15%, there is 91% power to detect a difference with a two-sided type I error of 0.05 between the groups. If only 70% enroll and other assumptions remain constant, there would be about 87% power to detect a difference.

Other examples are shown in Figure 3.

Three possible recruitment rates are shown in the left, middle and right panels. In each panel, the power to detect a difference, with a two-sided type I error of 0.05, between groups is shown on the vertical axis for different assumptions regarding the true underlying allergy rates in the consumer and avoider groups at month 144. In each panel contour lines display rates in consumers of 2%, 4%, 6%, 8% and 10% while the horizontal axis displays a range of rates in avoiders of 10 to 25%

#### **LEAP Siblings**

The sample size for LEAP siblings is based on observing as many individuals as is practical among those who can meet the eligibility criteria. Different sample sizes provide power to detect differences of varying amounts depending on how many individuals are available for analysis.

The primary endpoint for the sibling cohort is listed in section 3.2.

For protocol versions 1.0 and 2.0, we estimated that 222 younger siblings with at least one year of exposure to the LEAP intervention are potentially available from the LEAP avoidance arm and 207 from the LEAP consumption arm. In protocol version 3.0, we removed the criterion that younger siblings needed to have at least one year of exposure to the LEAP intervention. This resulted in an estimated 80 additional younger siblings to be available for recruitment into LEAP Trio. We aim to be able to detect an increase in the sensitization rate of individuals meeting the primary endpoint between 18.4% from the siblings in the consumption arm and 8.4% from the siblings in the LEAP avoidance arm.

These assumptions are derived from findings in a survey questionnaire regarding allergy among siblings: 9.2% among consumer siblings and 4.2%% among avoider siblings. The conversion rate from peanut allergy to sensitization [IgE  $\geq$  0.35, SPT  $\geq$ 3mm] within the LEAP avoidance group at 60 months was 1.95 fold. At 72 months, the conversion rate within the LEAP avoidance group was 2.05 fold. The conversion rate of two fold (an average of the 60 and 72 month rates) was chosen to estimate the sensitization rate in younger siblings. For example, if 90% of the available individuals are enrolled and assessed, the rate of subjects meeting the primary endpoint [IgE  $\geq$  0.35, SPT  $\geq$  3mm] is 8% in the siblings of LEAP avoiders, and the rate of those meeting the primary endpoint [IgE  $\geq$  0.35, SPT  $\geq$  3mm] is 17% in the siblings of LEAP consumers, there is 83% power to detect a difference with a two-sided type I error rate of 0.05 between the groups. If only 80% of the available individuals are enrolled and assessed and other assumption remain constant, there would be about 79% power to detect a difference and only 73% power if 70% of the available individuals are enrolled and assessed while the other assumptions remain constant.

Other examples are shown in Figure 4.

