## 1.3.2 Questionnaires to LEAP Families

To further investigate the anecdotal observations, local Ethics Committee approval for issuing a questionnaire (the 'LEAP and LEAP-On Sibling Peanut Allergy Questionnaire') was obtained in October 2013 through amendments to the LEAP Study (04/Q0403/13) and the LEAP-On Study (10/H0711/77). All LEAP participant families were then informed of the background to and need for completion of the LEAP and LEAP-On Sibling Peanut Allergy Questionnaire. Out of 640 families, 619 (97%) were contacted and of these, 600 (94%) provided informed consent and completed the questionnaire. Nineteen declined informed consent. 523 families had at least one more child in addition to the LEAP participant while 77 families did not have a LEAP sibling. In total, these consented families provided information for 746 siblings.

The LEAP and LEAP-On Sibling Peanut Allergy Questionnaire revealed a questionnairebased diagnosis of peanut allergy of 4.2% in younger siblings of the LEAP avoidance group participants and 9.2% in younger siblings of the LEAP consumption group participants (p-value of difference in proportions is 0.057 using a one-tailed Wald analysis). These findings therefore supported the original observation that early peanut introduction in high-risk children may have led to an increase in the rates of peanut allergy in the younger siblings of children who consumed peanut on the LEAP Study as compared to the younger siblings of LEAP participants who avoided peanut. However, similar to the anecdotal observations from LEAP families, these questionnaire-based findings may also have arisen due to ascertainment bias because the siblings of LEAP peanut avoiders are less likely to have been exposed to peanut and therefore have had less opportunity to manifest symptoms of peanut allergy. An additional source of uncertainty arises from the 78 younger siblings (56 in the avoidance group and 22 in the consumption group) for whom the questionnaire result was a 'don't know' outcome due to the fact that the sibling may never have eaten peanut or ever undergone peanut allergy testing.

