6. STUDY PARTICIPANTS

For all analyses that include treatment arm, LEAP participants will be assigned to the intervention (LEAP Consumers) or control group (LEAP Avoiders) according to the prior randomized treatment assignment from the LEAP study. Siblings and parents will be assigned to the intervention or control group based on the prior randomization of their LEAP participant sibling or child, respectively.

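### The sibling power of 83/79/73% treats about 509 younger siblings as independent, although the planned co-primary analysis is clustered by family and the endpoint also counts Ara h2

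*Protocol*

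**What the plan says.** Protocol 9.3 (LEAP Siblings) starts from protocol versions 1.0 and 2.0, where "we estimated that 222 younger siblings with at least one year of exposure to the LEAP intervention are potentially available from the LEAP avoidance arm". The matching figure for siblings of consumers is 207. Version 3.0 then dropped the one-year exposure requirement: "This resulted in an estimated 80 additional younger siblings to be available for recruitment into LEAP Trio". The arm split of these 80 is not given.

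The section aims to detect 18.4% in siblings of consumers against 8.4% in siblings of avoiders. Its worked example uses 17% and 8%. At 90% enrolled and assessed, "there is 83% power to detect a difference with a two-sided type I error rate of 0.05 between the groups"; at 80% and 70% the power is given as about 79% and 73%. The endpoint behind these rates is labelled as IgE ≥ 0.35 and SPT ≥ 3 mm. No within-family correlation, family size or design effect is mentioned.

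Protocol 9.2.1 plans a "logistic regression model with a random family effect included to account for the clustering of siblings within family units", and gives the analysis of several younger siblings as a further reason for it. SAP 8.2.2.2 repeats this. SAP section 6 adds: "Siblings and parents will be assigned to the intervention or control group based on the prior randomization of their LEAP participant sibling".

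Protocol 3.3.2 and SAP 8.2.2.1 define sensitization as meeting any one of three criteria. One of them, absent from the label in 9.3, is "Peanut specific IgE to individual peanut component Ara h2" at or above 0.1 kU/L.

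**The concern.** Treatment arm is fixed at family level. If sensitization is positively correlated between siblings, a second younger sibling adds less information than a sibling from a new family. A calculation that counts every sibling as independent then overstates power for the same pair of rates.

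This comparison is a co-primary safety question: did peanut consumption by the LEAP child raise sensitization in younger siblings? The sample is limited to the siblings who exist, so it cannot be enlarged to recover lost power. The stated power is the documents' only guide to how much reassurance a non-significant result would give, and it describes neither the planned analysis nor the endpoint as defined.

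**Working it through.** **Inputs from Protocol 9.3.** Younger siblings: 222 (avoidance) + 207 (consumption) + 80 (arm not stated) = 509. Rates: 8% and 17%. Two-sided α = 0.05. Enrolled fraction f = 0.9, 0.8, 0.7. Assumption: the 80 split evenly, giving 262 and 247.

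**Reproducing the stated power.** Pooled two-proportion z-test, with p̄ the weighted mean rate:

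power = Φ[(|p₁ − p₂| − 1.96 × SE₀) / SE₁], where SE₀² = p̄(1 − p̄)(1/n₁ + 1/n₂) and SE₁² = p₁(1 − p₁)/n₁ + p₂(1 − p₂)/n₂.

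At f = 0.9: n = 235.8 and 222.3, p̄ = 0.1237, SE₀ = 0.03078, SE₁ = 0.03077. Power = Φ[(0.09 − 0.0603)/0.03077] = Φ(0.965) = 83.3%.

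| Siblings available | Rates | 90% | 80% | 70% |
|---|---|---|---|---|
| Stated in 9.3 | 8% v 17% | 83 | 79 | 73 |
| 509, the 80 split evenly | 8% v 17% | 83.3 | 78.7 | 73.2 |
| 509, all 80 to avoiders | 8% v 17% | 82.7 | 78.2 | 72.9 |
| 509, all 80 to consumers | 8% v 17% | 82.1 | 77.3 | 71.4 |
| 429 only | 8% v 17% | 76.6 | 71.6 | 65.9 |
| 429 only | 8.4% v 18.4% | 82.6 | 78.0 | 72.4 |

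The even split matches all three points with no design effect. The last row comes within about a point, but it does not use the rates printed with the powers, and it is also unclustered.

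**Same method for LEAP participants.** Protocol 9.3 says that if 80% enrol, the consumer rate is 6% and "the true rate of allergy among LEAP avoiders at 144 months is 15%, there is 91% power to detect a difference"; at 70% enrolment it gives about 87%. The same test with 311 and 319 gives 91.2% and 87.2%. Independence is reasonable there: 640 participants (Protocol 3.1) came from 640 families (Protocol 1.3.2).

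**Allowing for clustering.** The usual approximation divides n by DE = 1 + (m_w − 1) × ICC. Here m_w is the size-weighted mean number of younger siblings per family (sum of squared family sizes over total siblings), and the ICC is on the observed binary scale. If a fraction q of families has two younger siblings and the rest have one, the mean is m = 1 + q and m_w = (1 + 3q)/(1 + q).

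Neither m nor the ICC is in the documents, so both are assumed. The only family-size data are in Protocol 1.3.2: "523 families had at least one more child in addition to the LEAP participant", with 746 siblings in total, so 746/523 = 1.43 per family. That counts older and younger siblings together, so it serves as an outer case.

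| Assumed m | m_w | ICC | DE |
|---|---|---|---|
| 1.15 | 1.26 | 0.1 | 1.03 |
| 1.25 | 1.40 | 0.3 | 1.12 |
| 1.15 | 1.26 | 0.5 | 1.13 |
| 1.43 | 1.60 | 0.5 | 1.30 |

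| DE | Rates | 90% | 80% | 70% |
|---|---|---|---|---|
| 1.03 | 8% v 17% | 82.2 | 77.5 | 71.9 |
| 1.13 | 8% v 17% | 78.6 | 73.7 | 67.9 |
| 1.30 | 8% v 17% | 72.7 | 67.7 | 61.9 |
| 1 (none) | 8.4% v 18.4% | 88.4 | 84.5 | 79.5 |
| 1.13 | 8.4% v 18.4% | 84.4 | 79.9 | 74.5 |

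For 8% versus 17% at 90% enrolment, power reaches 80% at DE = 1.09 and is lower beyond that.

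**Ara h2.** Adding an either-or criterion can only raise each arm's rate, but its effect on power depends on how. Illustrations without clustering: +2 points in both arms (10% v 19%) gives 78.4/73.5/67.8%; both rates × 1.1 (8.8% v 18.7%) gives 87.1/83.0/77.8%; both × 1.2 (9.6% v 20.4%) gives 90.2/86.6/81.8%.

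**The case against.** The arithmetic in 9.3 is not mistaken: its figures reproduce. They are a worked example for a sample set by availability, and the analysis models the clustering. The strongest point is that 8% versus 17% is narrower than the stated aim. At 8.4% versus 18.4% with 509 siblings, a design effect of 1.17 gives 83.1/78.6/73.0%, which is what the protocol prints. For that aim, the printed powers are not overstated unless the design effect exceeds about 1.17. Section 9.3 also sets no 80% target, and it already shows power down to 73%. The loss rests on assumed values, and it is about one point in the mildest case. Using the plain mean of 1.43 instead of the size-weighted one, an ICC of 0.5 gives 1.21, not 1.30. The Ara h2 gap has no known direction.

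Most of this stands as a limit on size. It does not rescue the statement itself: 9.3 ties its powers to 8% and 17%, and for those rates they describe independent siblings. That a wider difference would leave room for clustering is a coincidence the protocol neither states nor relies on. With data collection ending on 31 August 2022, the precision of the clustered estimate will in the end say more about a null result than any planning figure. That limits the consequence but does not make the stated power right.

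**Conclusion.** The concern holds. The stated sibling power is an independent-observations figure for about 509 younger siblings and does not belong to the planned family-clustered analysis. For 8% versus 17%, the overstatement runs from about 1 point (design effect 1.03) through about 5 (1.13) to about 10 or 11 in the outer case (1.30). These sizes depend on assumed family sizes and correlations. The direction depends only on the correlation within families being positive. The total of 509 and the even split are inferred from the text; the figures for siblings (Figure 4) and cohorts (Figure 1) could not be seen. At the wider stated aim, a moderate clustering loss leaves power at or above the printed values.

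Power for the three-criterion endpoint is not established in either direction. The Ara h2 omission should not be read as an overstatement. The primary analysis is sound on this point.

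**What to change.** In Protocol 9.3 (LEAP Siblings):

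- Restate power with DE = 1 + (m_w − 1) × ICC, with m_w calculated from the actual distribution of younger siblings per family, over a stated range of ICC on the observed binary scale. Do this for both 8% v 17% and 8.4% v 18.4%.
- Give the arm split of the 80 added siblings and the total used.
- Give assumed rates for the endpoint as defined in Protocol 3.3.2, with Ara h2 included, and correct the endpoint label.

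This changes text only. It needs family sizes, which the sibling questionnaire should supply, although the documents do not tabulate them. The cost is a somewhat less favourable stated power for the 8% v 17% example. Enrolment and the analysis stay as they are.
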